11.17.4 Average Time-on-Task

Average time on task at Week 6 and Week 8/EOS (and at other weeks as applicable) is calculated as the sum of the task time (calculated as mentioned in section 11.17.3) from each required session completed, divided by the number of required completed sessions at Week 6 and Week 8/EOS.

$$\text{Average Time - on - Task (minutes)} = \frac{\text{Sum of the task time from each required VR session completed at Week } X}{\text{Total number of completed required VR sessions}}$$

X is 1, 2, ..., 8.

Overall average Time-on-Task per session across the entire study will be calculated as

$$\text{Overall Average Time - on - Task (minutes)} = \frac{\text{Sum of the task time from each required VR session completed}}{\text{Total number of completed required VR sessions}}$$

11.17.5 Total Number of Active Days

Total number of active days across the study is the total number of days that subjects have at least VR session. If a subject has 3 sessions each week and 1 session per day, total number of active days is 24. Repeated session in the same day does not count.

11.17.6 LSAS Score and Subscales

The LSAS is a clinician administered instrument that assesses both anxiety and avoidance across a number of social situations. The scale consists of 24 items each depicting different social situations. The anxiety scale ratings range from 0 (no anxiety) to 3 (severe anxiety). The avoidance ratings also range from 0 (never avoid) to 3 (usually avoid). In addition to the anxiety and avoidance subscales, the

LSAS is further divided into two subscales for scoring, including social interaction (11 items) and performance situations (13 items).

Items dealing with socializing are:

- Talking to people in authority
- Going to a party
- Calling someone you don't know very well.
- Talking with people you don't know very well.
- Meeting strangers
- Being the center of attention
- Expressing a disagreement or disapproval to people you don't know very well.
- Looking at people you don't know very well in the eyes.
- Returning good to a store
- Giving a party
- Resisting a high pressure salesperson

Items dealing with performance are:

- Telephoning in public
- Participating in small groups
- Eating in public places
- Drinking with others in public places
- Acting, performing or giving a talk in front of an audience
- Working while being observed
- Writing while being observed
- Urinating in a public bathroom
- Entering a room when others are already seated.
- Speaking up at a meeting
- Taking a test
- Giving a report to a group

- Trying to pick up someone.

An LSAS total score along with six additional scores based on anxiety and avoidance is derived at Baseline, Week 2, Week 4, Week 6 and Week 8: total fear, fear of social interaction, fear of performance situations, total avoidance, avoidance of social interaction, and avoidance of performance situations.

11.17.6.1 LSAS Total Score

Total LSAS score is calculated for each subject at each visit by taking the sum of both anxiety and avoidance score of all 24 items of the scale. Scores may range from 0 to 144.

11.17.6.2 Total Fear

Total fear is evaluated using total fear subscore which is calculated for each subject at each visit by taking the sum of fear scores of all 24 items. Scores range from 0 to 72.

11.17.6.3 Fear of Social Interaction

Fear of social interaction is evaluated using fear of social interaction subscore which is calculated for each subject at each visit by taking the sum of fear scores of the items dealing with socializing. Scores range from 0 to 33.

11.17.6.4 Fear of Performance Situations

Fear of performance is evaluated using fear of performance subscore which is calculated for each subject at each visit by taking the sum of fear scores of the items dealing with performance. Scores range from 0 to 39.

11.17.6.5 Total Avoidance

Total avoidance is evaluated using total avoidance subscore which is calculated for each subject at each visit by taking the sum of avoidance scores of all 24 items. Scores range from 0 to 72.

11.17.6.6 Avoidance of Social Interaction

Avoidance of social interaction is evaluated using avoidance of social interaction subscore which is calculated for each subject at each visit by taking the sum of avoidance scores of the items dealing with socializing. Scores range from 0 to 33.

11.17.6.7 Avoidance of Performance Situations

Avoidance of performance situation is evaluated using avoidance of performance situation subscore which is calculated for each subject at each visit by taking the sum of avoidance scores of the items dealing with performance. Scores range from 0 to 39.

11.17.7 Total PHQ-9 Score

The PHQ-9 is the depression module, which scores each of the 9 DSM criteria as “0” (not at all) to “3” (nearly every day). Total PHQ-9 score will be assessed at Baseline, Week 2, Week 4, Week 6 and Week 8.

Total PHQ-9 score is calculated for each subject at each visit by taking the sum of score of all 9 items of the scale. Scores may range from 0 to 27.

11.17.8 Responder Rate

Responder rate based on the CGI-I score is the proportion of responders at Week 8. Responders are subjects who rated 1 (very much improvement) or 2 (much improvement) in CGI-I at Week 8.

$$\text{Responder Rate} = \frac{\text{Number of responders at Week 8 in a treatment group}}{\text{Total number of subjects in that treatment group in mITT}}$$

11.18 Self-Evident Corrections

In some instances, spelling errors may be corrected in programs for 'Other, Specify' fields (free text). These will be reconciled and confirmed with sponsor before database lock.

12 Statistical Analyses

Planned or Actual treatment groups will use the following conventions:

- Enrolled Population - Planned treatment group
- FAS Population – Planned treatment group
- Safety Population – Actual treatment group
- ITT Population – Actual treatment group
- Per-protocol Population – Actual treatment group

12.1 Subject Disposition

The number and percentage of subjects in screened, Enrolled Population, FAS population, Safety Population, Per-Protocol population and ITT population will be presented by treatment groups and total. Percentages for FAS population is based on Enrolled Population and percentages for all the other populations will be based on FAS population.

Number and percentage of subjects who completed the study, number and percentage of subjects who failed screening along with their reasons, number and percentage of subjects who terminated the study early along with their reasons will be summarized separately by treatment group and total. Reasons for screen failure will be displayed as in CRF. Percentages will be based on all screened subjects who signed ICF. Reason for discontinuation will be displayed in the descending order of "Total" column and percentages will be based on FAS population.

A flow diagram of subject disposition (CONSORT flow diagram) illustrating the progress of subjects throughout the study from screening to study completion/discontinuation will be provided.

Note that Enrolled Population and FAS population will be displayed by planned treatment and all other populations will be displayed by actual treatment.

Subject disposition information, status of inclusion exclusion criteria and subjects excluded from ITT analysis will be listed by subject who are screened.

Above analysis details are specified in DDP Table 14.1.1.1, Table 14.1.1.2, Figure 14.1.1.1, Listing 16.2.1.1, Listing 16.2.1.2 and Listing 16.2.3.1

12.2 Important Protocol Deviations

Number and percentage of subjects with any important protocol deviations and number of important protocol deviation events will be summarized by treatment groups and total based on FAS population. Important protocol deviation categories will be displayed in descending order of the “Total” column.

All the protocol deviations will be listed by subject who enrolled in the study.

Above analysis details are specified in DDP Table 14.1.2.1 and Listing 16.2.2.1.

12.3 Demographic and Baseline Clinical Characteristics

The following summaries will be presented by treatment groups and total based on Intent-to-Treat Population and Per-Protocol Population (as per ICH E3 Guidelines), unless otherwise specified.

Demographic characteristics and clinical characteristics at baseline will be summarized as follows:

- Demographic characteristics:
 - Age (years): summary statistics
 - Age categories
 - <18 years, ≥18 to ≤40 years, >40 to ≤65 years, >65 years
 - Sex assigned at birth: Male, Female
 - Ethnicity: Hispanic or Latino, Not Hispanic or Latino, Not Reported, Unknown
 - Race: American Indian or Alaska Native, Asian, Black or African American, Native Hawaiian or Other Pacific Islander, White, Other, Not Reported
- Clinical characteristics

The results collected at the baseline, as per section 11.10, will be considered as the baseline clinical characteristics. Following variables will be presented:

- CEQ score
- Credibility score
- Expectancy score
- Total LSAS score
- CGI-S score
- PHQ-9 Score

Subject demographics will be listed by all subject who are screened. Baseline Clinical Characteristics will be listed by subject who are enrolled.

Above analysis details are specified in DDP Table 14.1.3.1, Table 14.1.3.2, Listing 16.2.4.1, Listing 16.2.6.1, Listing 16.2.6.3.1, Listing 16.2.6.3.2, Listing 16.2.6.4, Listing 16.2.6.5.

No statistical testing will be carried out for demographic or baseline clinical characteristics.

12.4 Psychiatric and Medical History

Number and percentage of subjects with any psychiatric or medical history and number of events will be summarized by treatment groups and total based on safety population. The same will be classified by System Organ Class (SOC) and Preferred Term (PT). The SOC and PT will be displayed in the descending order of frequency in “Total”. Medical history will be coded using the Medical Dictionary for Regulatory Activities (MedDRA) version 26.0 or Higher.

The summary will be presented by following categories:

- Comorbid psychiatric conditions
- General Medical History separately

Above analysis details are specified in DDP Table 14.1.5.1.

Psychiatric details collected for subject who are screened will be listed in DDP Listing 16.2.4.2.1

Psychiatric and Medical History will be listed by subject and body system based on Safety Population. List details are specified in DDP: Listing 16.2.4.2.2

12.5 Prior and Concomitant Medications

Number and percentage of subjects who have taken any prior / concomitant medication and number of medications will be summarized by treatment groups and total based on safety population. The same will be presented by Therapeutic Main group (ATC Level 3) and Preferred Term. The therapeutic main group and preferred term will be displayed in the descending order of frequency in “Total”. Medications will be coded using the World Health Organization’s Drug-Dictionary (WHODrug) version Mar-2023 or later.

The summary will be presented for prior and concomitant medications separately.

Above analysis details are specified in DDP: Table 14.1.6.1 and Table 14.1.6.2

All medications will be listed by subject and therapeutic subgroup.

Above analysis details are specified in DDP: Listing 16.2.4.3

12.6 Psychotropic Medications

Number and percentage of subjects who have taken any psychotropic medication 12 hours prior to a visit and number of medications will be summarized by treatment groups and total based on safety population. Only psychotropic medication taken 12 hours prior to a visit will be summarized. The same will be presented by Therapeutic Main group (ATC Level 3) and Preferred Term. The therapeutic main group and preferred term will be displayed in the descending order of frequency in “Total”.

Medications will be coded using the World Health Organization's Drug-Dictionary (WHODrug) version Mar-2023 or latest.

All medications will be listed by subject and therapeutic subgroup on Safety Population. Above analysis details are specified in DDP Table 14.1.6.3 and Listing 16.2.4.4

12.7 Study and Treatment Duration

The subject will be encouraged to engage in minimum three VR sessions per week, for a period of 8 weeks. The following analysis will be summarized based on the Safety Population.

Study duration and treatment duration of VR intervention participation to the study will be summarized as a continuous variable as well as in categories by treatment groups. The categories for durations are >0 – 2, >2 – 4, >4 – 6, and >6 – 8 weeks.

Above analysis details are specified in DDP Table 14.1.7.1.

12.8 Efficacy Analyses

12.8.1 Primary Efficacy Analysis

12.8.1.1 Descriptive Summaries

The following summaries will be presented by treatment groups based on ITT and PP population. For Credibility, Expectancy, Total CEQ Score separately, descriptive summary of observed and change from baseline results for expectancy and credibility score will be summarized by visit (Baseline, Week 6 and Week 8/EOS). Also, descriptive summary of the total CEQ score and score for each item will be summarized based on treatment groups and visit. Mean Credibility and Expectancy scores will be plotted using line plots by visit. All listings are based on enrolled population.

12.8.1.2 Inferential Summaries

The independent t-test or Mann-Whitney U test will be used to check the significant difference between treatment groups. Exact p-value obtained will be presented in summary tables.

Normality test

Shapiro-Wilk test will be performed to test the normality of the two treatment groups and p-value will be interpreted. The test also assumes homogeneity of variances between the two treatment groups. Either one of the following tests will be performed:

- If Shapiro Wilk Test p-value > 0.05 then parametric T-Test will be used
- If Shapiro Wilk Test p-value < 0.05 then Mann-Whitney test will be used

Independent t-tests

Independent t-test will be used to compare mean scores (Observed and change from baseline scores) between treatment groups by visit.

Assumptions

- The samples are independent of one another.
- The sample is normally distributed within each of the two treatment groups.
- The variance should be homogeneous in the two treatment groups.

Reference SAS Program:

T-Test

```
proc ttest data = <INDATA>;
  class <TREATMENT>;
  var AVAL;
run;
```

Mann-Whitney test

```
proc npar1way data=<INDATA> wilcoxon;
  class <TREATMENT>;
  var AVAL;
run;
```

Hypothesis:

H_0 : Mean of parameter is the same in two treatment groups.

vs.

H_1 : Mean of parameter is not the same in two treatment groups.

Supportive analysis of the same will be presented for ITT and Per-Protocol population in a separate table.

Above analysis details are specified in DDP: Table 14.2.1.1, Table 14.2.1.2, Table 14.2.1.3, Table 14.2.1.4, Table 14.2.2.1, Table 14.2.2.2, Table 14.2.2.3, Table 14.2.2.4, Figure 14.2.2.5.

All CEQ scores will be listed in Listing 16.2.6.1

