## 4.3. Intervention Use Justification

The present pilot study is set to inform a subsequent RCT evaluating the clinical effectiveness and safety of BVR-100 intended to support registration. Key design parameters of the present pilot study will be generally aligned with that of the subsequent planned RCT, including the study duration, main effectiveness outcomes, inclusion and exclusion criteria, study visits, and subject monitoring.

The present study aims to evaluate the credibility and expectation of benefit of BES-100 vs BVR-100 as a proxy for subject blinding. In line with FDA recommendations, study endpoints will also include an evaluation of time-on-task and drop-out rates (also referred to as subject retention) at end-of-study (EOS). Like the subsequent RCT, this 8-week, 2-arm, double-blinded pilot RCT will compare both BES-100 and BVR-100 interventions. Subjects meeting the diagnostic criteria for SAD and a Liebowitz Social Anxiety Scale (LSAS) score at Screening of  $\geq 70$  will be randomly allocated to the BVR-100 or BES-100 groups and asked to complete an at-home, self-guided VR intervention for 8-weeks. In order to obtain preliminary evidence of effectiveness in a manner that is aligned with the primary and secondary endpoints planned in

the subsequent RCT, SAD fear and avoidance symptoms and overall symptom improvement will be assessed using the LSAS and the CGI scales, in addition to the self-reported PGI-I. Self-reported and clinician-administered assessments will be administered at Baseline, Week 2, Week 4, Week 6, and Week 8 (EOS).

Because of the exploratory nature of the study, no formal hypothesis testing will be used to assess clinical benefit (or lack thereof). The sample size is intended to support the reliable evaluation of treatment credibility, time-on-task, and drop-out rates across study arms.

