### 15.2. Analysis Populations

The effectiveness analyses will be based on the modified Intent-to-Treat (mITT) population, which includes all subjects who are randomized, have completed at least one VR session, and have a Baseline and at least one post-Baseline effectiveness measurement in CEQ. Additional analysis of the Per-Protocol (PP) population (defined as all subjects who have completed the 8-week intervention period without any important protocol deviations) is supportive, while the mITT population will be the primary analysis population. The primary effectiveness endpoint must achieve significance in the mITT to preserve type I error for the secondary endpoint.

The safety assessments will use the Safety population, which includes all subjects who are randomized and have completed at least one VR session.

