### **15.4.2. Effectiveness Analyses**

No formal hypothesis testing relating to primary, secondary, or exploratory outcomes is planned because this is a pilot study.

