#### **15.4.2.1. Analysis of Primary Endpoint**

Descriptive statistics will be used to estimate group differences in the CEQ at Baseline and at Weeks 6 and 8. Exploratorily, CEQ scores differences between groups will be computed using Student's *t* tests will be analyzed.

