8.1 General Conventions

Level of significance for statistical tests will be 0.05 two-sided. All analyses will be done using SAS (version 9.4, SAS Institute Inc., Cary, NC, USA).

Safety endpoints will be analyzed in a descriptive manner. Continuous data will be reported using the following descriptive statistics:

- Number of observations (n)
- Mean and Standard deviation (SD)
- Median
- Minimum (min) and Maximum (max)
- 25th percentile and 75th percentile

Categorical data will be presented using frequency (n = number of subjects; m = number of events) and percentage (%).

Listings will be provided for all data recorded in eCRF to study subject profiles. All listings will be sorted by treatment, subject ID and date (if applicable). Unscheduled visit data will only be listed and not included in summaries.

All p-values will be displayed to four decimal places, with p-values less than 0.0001 presented as '<0.0001' and p-values greater than 0.9999 presented as '>0.9999'. Minimum and maximum values will be reported in the units of collection with 3 decimals being maximum value; the mean, median, 25th percentile and 75th percentile will be presented with 1 decimal place more and the standard deviation 2 decimal places more than the units of collection. Percentages for categorical summaries will be represented to 1 decimal place.

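### The SAP commits to a p-value, but not to a between-arm difference with a confidence interval, for the CEQ comparison that serves as the proxy for blinding

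*SAP*

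**What the plan says.** Protocol 4.3 gives the purpose of the comparison: "The present study aims to evaluate the credibility and expectation of benefit of BES-100 vs BVR-100 as a proxy for subject blinding". Section 7.3.1 repeats it and adds that the pilot is to inform a later registration trial.

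Protocol 15.4.2.1 sets out the analysis: "Descriptive statistics will be used to estimate group differences in the CEQ at Baseline and at Weeks 6 and 8". Student's t-tests are added as exploratory.

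The SAP has two layers for the CEQ:

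- **12.8.1.1, per arm:** "For Credibility, Expectancy, Total CEQ Score separately, descriptive summary of observed and change from baseline results", by visit. SAP 8.1 lists n, mean and SD among the standard descriptive statistics.
- **12.8.1.2, between arms:** a t-test or Mann-Whitney test "will be used to check the significant difference between treatment groups. Exact p-value obtained will be presented in summary tables". The choice between them is automatic: "If Shapiro Wilk Test p-value < 0.05 then Mann-Whitney test will be used". The stated null hypothesis is equality of means. SAP 8.1 sets the level: "Level of significance for statistical tests will be 0.05 two-sided".

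The SAP appendix table lists only a descriptive summary and an independent t-test for the CEQ. SAP 12.8.1.2 refers to a Data Display Plan for table details.

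On the role of significance, protocol 15.2 says "The primary effectiveness endpoint must achieve significance in the mITT to preserve type I error for the secondary endpoint", while protocol 15.4.2 says "No formal hypothesis testing relating to primary, secondary, or exploratory outcomes is planned because this is a pilot study".

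**The concern.** A test of equal means can find a difference but cannot show that two arms are alike. Here likeness is what the sponsor hopes to see, because BES-100 is a candidate sham for the registration trial. The useful question is how large a BES-100 deficit in credibility or expectancy the data still allow. A p-value does not answer that; a difference with its confidence interval does.

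The Shapiro-Wilk step adds a second problem. When it selects Mann-Whitney, the reported p-value no longer tests the stated null hypothesis about means. The selection can also differ between scores and visits, so the p-values need not refer to the same quantity. The Mann-Whitney reference code in the SAP requests no estimate of the difference.

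At stake is the reading of the pilot's primary endpoint. A column of non-significant p-values could be taken as support for the sham when the sample is too small to say so.

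**Working it through.** **1. The plan's own figure.** SAP 4.2 inflates 15 per arm for 25% attrition: 15 / (1 − 0.25) = 20 per arm, 40 in total. This reproduces. The documents state no power for the CEQ comparison.

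**2. Inputs.**

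- Two-sided alpha 0.05 (SAP 8.1); 1:1 allocation (SAP 4.3).
- n per arm: 20 recruited and 15 after attrition (SAP 4.2). 26 is half of the 52 subjects in the ITT population (SAP 13). 12 is half of the 24 who had a baseline and at least one post-baseline CEQ at the 19 January 2024 data cut (SAP 13).
- The even splits are assumed. CEQ n per visit is not given, and SAP 9.1.1 rules out imputation. Thus 26 would need complete CEQ data, and 12 is not a strict lower bound for a single visit.
- True BES-100 deficit d: assumed at 0.3, 0.5 and 0.7 SD, because the documents give no CEQ effect, SD or margin. Normal data and equal SDs are assumed.

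**3. Chance of a non-significant result.** This is 1 − power of the two-sample t-test, from the noncentral t distribution with 2n − 2 degrees of freedom and noncentrality d × √(n/2). For example, at d = 0.5 and n = 26 the noncentrality is 0.5 × √13 = 1.803 and the result is 57.6%.

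| n per arm | d = 0.3 | d = 0.5 | d = 0.7 |
|---|---|---|---|
| 12 | 89.2% | 78.4% | 62.5% |
| 15 | 87.5% | 73.8% | 54.3% |
| 20 | 84.8% | 66.2% | 42.2% |
| 26 | 81.4% | 57.6% | 30.3% |

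A 20,000-run simulation of the Shapiro-Wilk selection on normal data at d = 0.5 gives 78.8% at 12 per arm and 57.0% at 26, so the selection step barely changes the figures. Uneven splits change little at d = 0.5: 30/22 gives 58.4% and 14/10 gives 78.9%.

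**4. Width of the interval that is not named.** Half-width in SD units = t(0.975, 2n − 2) × √(2/n).

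- n = 12: 2.074 × 0.4082 = 0.85
- n = 15: 2.048 × 0.3651 = 0.75
- n = 20: 2.024 × 0.3162 = 0.64
- n = 26: 2.009 × 0.2774 = 0.56

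**5. What a non-significant result would leave open.** If the arms are truly equal and the test is non-significant, the 95% CI still includes a 0.5 SD BES-100 deficit about 80%, 75%, 67% and 58% of the time at 12, 15, 20 and 26 per arm (pooled t, 200,000 runs). The whole CI lies within ±0.5 SD in about 1% of trials at 26 per arm, and in fewer at the smaller sizes.

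**The case against.** The case against is substantial, and most of it limits the reach of the point.

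- **The estimate may already be there.** SAP 12.8.1.2 sends the table details to the Data Display Plan, and the PROC TTEST step it specifies produces the difference and interval. What is certain is only that the SAP text is silent. This stands.
- **Little information is lost.** With n, mean and SD per arm and visit, a reader can compute both the difference and its interval. This stands too: the gap is in what the SAP commits to show, not in the data.
- **A reader might infer that the SAP cancelled the protocol's estimate.** The documents do not support that. SAP section 2 overrides the protocol only where the two differ, and SAP 13 lists no such change. The omission may be unintended.
- **A reader might infer that the sponsor will take non-significance as proof of blinding.** No section says so. The documents are silent on how such a result will be read, and low power is expected in a pilot that disclaims formal testing.
- **A reader might quote 58% to 78% as the size of the problem.** Those figures belong to an assumed 0.5 SD. Across the assumed 0.3 to 0.7 SD the range is 30% to 89%.
- **A reader might infer from protocol 15.2 that a well-matched sham would make the trial fail.** That sentence conflicts with protocol 15.4.2, but it looks inoperative. The SAP takes precedence on discrepancies, marks multiplicity as not applicable, removes the mITT population and analyses the secondary endpoints descriptively. It is a separate contradiction to tidy up.

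The objection does not dispose of the mismatch between question and output. The only between-arm result the SAP text promises comes from a test that cannot address comparability.

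**Conclusion.** The point holds in a limited form. For a comparison where similarity is the favourable outcome, the SAP text commits to per-arm summaries and a difference-test p-value, and names no between-arm difference or confidence interval. When Mann-Whitney is selected, the p-value does not match the stated hypothesis about means.

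The size depends on assumptions: true deficits of 0.3 to 0.7 SD, 12 to 26 per arm in even splits, normal data and equal SDs. Under these, non-significance occurs 30% to 89% of the time when a deficit exists, with a CI half-width of about 0.56 to 0.85 SD. This is worth correcting because it concerns the primary endpoint. It is a defect of committed reporting and interpretation, not a lost analysis, and the Data Display Plan may already meet part of it.

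**What to change.** In SAP 12.8.1.2 and the appendix table:

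- Report the BVR-100 minus BES-100 mean difference with its 95% CI for credibility, expectancy and total CEQ at each visit, whatever Shapiro-Wilk shows. Take it from the PROC TTEST step already specified, and state whether the pooled or unequal-variance interval is used.
- Keep the t-test or Mann-Whitney p-value as secondary output.
- State that a non-significant result will not be read as comparable credibility.
- If the Data Display Plan already shows the difference and interval, say so in the SAP text.

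Separately, delete the protocol 15.2 sentence on achieving significance, or reconcile it with protocol 15.4.2.

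The cost is some SAP wording, added table columns and a protocol clarification; no new data are needed. Three scores at three visits give 3 × 3 = 9 intervals for observed scores, to be read descriptively. The drawback is that the intervals will be wide: they show what the pilot cannot rule out but cannot establish close equivalence.

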12.9.2 Inferential Summaries

The independent t-test or Mann-Whitney U test will be used to check the significant difference between treatment groups. Exact p-value obtained will be presented in summary tables. Normality test will be performed based on the methods as described in section 12.8.1.2.

Above analysis details are specified in DDP: Table 14.2.4.1, Table 14.2.4.2, Table 14.2.4.3, Table 14.2.5.1, Table 14.2.5.2, Figure 14.2.4.1.

Fisher's Exact Test for Independence of Responders

Since sample size of the responders is expected to be small, the association of responders between the treatment groups will be investigated using Fisher's exact test. Fisher's exact test will be used to compare the proportion of respondents between the treatment groups.

Descriptive statistics and p-values from the test will be provided.

Assumptions

- Variables are categorical.
- All observations are independent.

Reference SAS Program:

```
proc freq data = <INDATA>;
  tables <TESTVAR1>*<TESTVAR2> / fisher;
run;
```

Hypothesis:

H_0 : There is no association between treatment group and responders rate.

vs.

H_1 : There is association between treatment group and responders rate.

Above analysis details are specified in DDP Table 14.2.6.1, Listing 16.2.6.3.1, Listing 16.2.6.3.2, Listing 16.2.6.4, Listing 16.2.6.5, Listing 16.2.6.6, Listing 16.2.6.7

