Credibility / Expectancy Questionnaire (CEQ) scores	ITT Population	Primary: Descriptive summary, Independent t-test
	Per-Protocol Population	Supportive: Descriptive summary, Independent t-test
Secondary Endpoints		
Subject Retention Rate	ITT Population	Descriptive summary
Time-on-task		Descriptive summary
Exploratory Endpoints		
LSAS Overall & Subscores	ITT Population	Descriptive summary, Independent t-test
Responder Rate		Descriptive summary, Fisher's exact test
CGI-S Score		Descriptive summary
CGI-I Score		Descriptive summary
PGI-I Score		Descriptive summary
PHQ-9 Score		Descriptive summary
Safety Endpoints		
Adverse Events	Safety Population	Descriptive summaries on overall AE, relationship, severity etc.
C-SSRS		Descriptive summary

17 Change Log

Version	Author	Change Date	Description	Reviewer	Review Date
1.00	[REDACTED]	31-Jan-2024	First Approved Version	[REDACTED]	31-Jan-2024

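### The Shapiro-Wilk gate in SAP 12.8.1.2 lets the primary CEQ table mix two tests under one hypothesis of equal means, and does not guarantee the 5% level when the arms differ in spread or skew

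*SAP*

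**What the plan says.** SAP 12.8.1.2 gives two branches: "If Shapiro Wilk Test p-value > 0.05 then parametric T-Test will be used" and "If Shapiro Wilk Test p-value < 0.05 then Mann-Whitney test will be used". The comparisons are set out as follows: "Independent t-test will be used to compare mean scores (Observed and change from baseline scores) between treatment groups by visit". SAP 12.8.1.1 handles Credibility, Expectancy and the CEQ total separately. After the code for both tests, a single null hypothesis is printed: "Mean of parameter is the same in two treatment groups". SAP 8.1 adds: "Level of significance for statistical tests will be 0.05 two-sided".

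SAP 12.9.2 carries the rule over to the exploratory scores: "Normality test will be performed based on the methods as described in section 12.8.1.2".

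Other places name the t-test alone. The appendix (SAP section 16) gives "Primary: Descriptive summary, Independent t-test" for CEQ in the ITT population, and lists the t-test alone for the per-protocol analysis and for LSAS. Protocol 15.4.2.1 says "Exploratorily, CEQ scores differences between groups will be computed using" Student's t tests. SAP section 13, which lists changes from the protocol, does not mention a Mann-Whitney branch for CEQ.

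The SAP does not say:
- whether Shapiro-Wilk is run per arm, on pooled data or on residuals;
- what happens if the two arms give different answers, or if p equals 0.05 exactly;
- which line of the PROC TTEST output is reported if variances differ.

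**The concern.** Three things follow from the wording.

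1. **Mixed tests.** No single overall choice of test is stated, so each score-by-visit cell picks its own. Neighbouring p-values in the primary table can then answer different questions under one printed hypothesis. Mann-Whitney compares whole distributions, through the chance that a score from one arm exceeds a score from the other. It is a test of means only under extra assumptions about shape, and the SAP states none.
2. **Dependence on n.** Shapiro-Wilk gains power as n grows, so the same score shape tends to stay with the t-test in a small cell and go to Mann-Whitney in a larger one. CEQ counts may differ sharply between visits: SAP section 13 reports that only 24 of 52 safety subjects met the mITT definition, because CEQ data were missing.
3. **Level.** If the arms have equal means but different spread or skew, the Mann-Whitney branch can reject more often than 5% under the printed hypothesis.

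The protocol (4.3 and 7.3.1) uses credibility and expectancy as a stand-in for subject blinding and means the pilot to inform a registration trial. Readers will use these p-values to judge whether the sham is as credible as the active program.

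**Working it through.** **The plan's own arithmetic.** SAP 4.2 inflates 15 per arm for 25% attrition: 15 / (1 - 0.25) = 20 per arm, 40 in total. This reproduces. The documents give no CEQ SD, shape or arm counts, so everything below rests on assumptions.

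**Inputs.**
- Two-sided level 0.05 (SAP 8.1).
- Factor score: three items rated 1-9 (SAP 11.17.1), so 3 to 27.
- Arm sizes: 26 (52 ITT subjects at 1:1), 20 (planned) and 12 (24 subjects at 1:1). Equal arms are assumed.
- Cells: 3 scores x 3 visits = 9 observed. Adding 3 scores x 2 changes gives 15, if change is also tested for the total.
- Gate: Shapiro-Wilk in each arm, Mann-Whitney if either p < 0.05, otherwise pooled t. This 'either arm' version is an assumption. Applying the test to within-arm residuals gave similar results.

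**How often the table mixes tests.** With exactly normal, independent cells, the chance that at least one of nine cells switches is 1 - 0.95^18 = 0.60 (two arms x nine cells). Simulation used normal scores rounded to integers, with correlation 0.7 between factors and 0.3-0.8 between visits. Mann-Whitney was chosen in 12-14% of cells. Both tests appeared in about 55-65% of trials over 9 cells and 77-87% over 15.

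**Level of the rule.** There were 30,000 trials per scenario (Monte Carlo SE about 0.13 points at 5%). Apart from the normal case (mean 18, SD 4, rounded), score = round(3 + 24B), with B ~ Beta(a, b). For a/(a+b) = 0.7:
- mean = 3 + 24 x 0.7 = 19.8
- SD = 24 x sqrt(0.21 / (a+b+1)), which gives 5.5 for a+b = 3, 3.3 for 10, 6.35 for 2 (6.4 after rounding scores to integers) and 2.4 for 20

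Entries are for 26 / 20 / 12 per arm.

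| Scenario | Mann-Whitney chosen, % | SAP rule rejects, % | Welch rejects, % |
|---|---|---|---|
| Same normal in both arms | 14 / 13 / 12 | 5.2 / 5.1 / 5.3 | 5.0 / 4.9 / 5.1 |
| Same skewed Beta(4, 1.7) in both arms | 51 / 39 / 23 | 5.4 / 5.3 / 5.3 | 5.2 / 4.9 / 5.0 |
| Equal means, SD 5.5 vs 3.3, medians 21 vs 20 | 68 / 52 / 29 | 9.5 / 8.5 / 6.9 | 5.0 / 5.2 / 5.2 |
| Equal means, SD 6.4 vs 2.4, medians 22 vs 20 | 86 / 72 / 44 | 16.8 / 14.9 / 11.5 | 5.4 / 5.7 / 6.2 |

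Separate runs with other assumed 3-27 shapes and equal means gave:
- SD 4.6 vs 3.5: 5.4-6.3%.
- SD 5.2 vs 3.1: 9.8%, 8.8% and 7.9% at 26, 20 and 12 per arm (Welch 4.9%, 5.0%, 5.5%; 4,000 trials).
- SD 5.7 vs 3.1: 11.9% at 26 per arm and 8.4% at 12 (Welch 5.3% at 26).

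**Reading.** The second row shows the dependence on n: one score shape, identical in both arms, goes to Mann-Whitney in 23% of trials at 12 per arm and 51% at 26. Pooled t on those data rejects in 4.9-5.2% of trials, so the gate protects nothing there. In the last two rows the excess comes from the Mann-Whitney branch: pooled t alone stays at 5.1-6.6%.

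**The case against.** - **A reader might infer that the rule loses its 5% level in general.** It does not. With one distribution in both arms it stays at 5.1-5.4% in the runs above. The loss needs equal means together with unequal spread or skew, and it is small when the difference is mild or n is near 12 per arm. Since missing CEQ values are not imputed (SAP 9.1.1), 26 per arm is a ceiling rather than an expectation at Weeks 6 and 8.
- **A reader might infer that a sound sham would be wrongly rejected.** In the inflated scenarios the arms do differ in distribution, medians included. The rejection is an error only against the printed hypothesis of means. The documents make no p-value the criterion for accepting the sham. Protocol 15.4.2 plans no formal testing, 15.4.2.1 calls the CEQ comparison exploratory, and full descriptive summaries are given. Still, SAP 8.1 sets a 0.05 level and 12.8.1.2 speaks of significance, so the p-values will be read.
- **A reader might see an omission in the lack of an EXACT statement in the Mann-Whitney code, given the promise of exact p-values.** That promise covers the t-test too, and more likely means that the actual p-value is printed. Nothing should be built on it.
- **The protocol's t-test is not a live conflict.** SAP section 2 gives the SAP precedence. The mismatch between 12.8.1.2 and the SAP's own appendix is one, and precedence over the protocol does not resolve it.
- **Pooled versus Welch hardly matters with equal arms.** That is correct on these figures. Preferring a test of means to Mann-Whitney for a bounded sum score is partly judgement. What needs correcting is that the data pick the test while the hypothesis stays fixed.

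**Conclusion.** The point holds in conditional form. Under SAP 12.8.1.2 the primary CEQ table can, and with nine or more cells probably will, combine two tests under one hypothesis that only one of them tests. The gate is not specified well enough to program, its outcome depends on n, and the appendix contradicts it.

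The 5% level is kept to within about half a point when the arms share one distribution. It is not guaranteed when means are equal and spread or skew differ: about 5-6% for mild differences, 7-12% for SDs near 5.5 versus 3.2, and up to about 17% in a strong case, across 12-26 per arm. Welch stays at about 5-6%. These rates assume 3-27 score shapes, equal arms and the 'either arm' gate.

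The consequence is limited to how the printed credibility and expectancy p-values are interpreted. No confirmatory error rate is at stake, and the descriptive summaries are unaffected.

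**What to change.** 1. Delete the Shapiro-Wilk gate from 12.8.1.2 and the reference to it in 12.9.2.
2. Use one pre-stated test of means in every CEQ cell: Welch's t-test (the Satterthwaite line of the PROC TTEST output already coded), with a 95% CI for the mean difference.
3. Report Mann-Whitney for all the same cells as one labelled sensitivity analysis, with its own hypothesis about distributions.
4. Make 12.8.1.2, 12.9.2 and the appendix name the same tests, and record the choice in SAP section 13.

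The cost is SAP wording, with less programming than the two-branch rule needs. The downside is that Welch may have slightly less power than Mann-Whitney if scores are strongly skewed. The sensitivity analysis covers that.
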